	
 1. Diagnosis of probable or definite ALS according to the revised El Escorial criteria, with bulbar onset of disease, familial or sporadic form, 2. Onset of symptoms \leq 18 months prior to screening, as reported by the patient, 3. Adult males or females, aged at least 18 years old, 4. SVC $>$ 60% of predicted value for age and sex, 5. ALSFRS-R score \geq 36, 6. Treatment with riluzole 100 mg/day, at stable dose since at least one month and well tolerated, 7. Male or female patient of childbearing potential¹ who agrees to use highly effective mechanical contraception methods (sexual abstinence, intrauterine device, bilateral tubal occlusion, vasectomised partner) throughout the study, and for 3 months after the end of the treatment, 8. Patient who read, understood and signed the informed consent form (ICF), 9. Patient who is willing to adhere to the study visit schedule and is capable to understand and comply with protocol requirements.
Exclusion criteria:	
A patient will not be eligible for inclusion in this study if at least one of the following criteria applies:
 
 1. Known other significant neurological disease(s), 2. Serious illness(es) or medical condition(s) (e.g. unstable cardiac disease, cancer, hematologic disease, hepatitis or liver failure, renal failure) that is not stabilised or that could require hospitalisation and may jeopardise the participation in the study, 3. Abnormal renal function at screening defined as estimated glomerular filtration rate (eGFR) $<$ 60 mL/min/1.73m², 4. Abnormal liver function at screening defined as total bilirubin levels $>$ 1.5 ULN, and/or AST and/or ALT $>$ 3 ULN, 5. Neutropenia (ANC $<$ 1.5 x 10⁹/L) at screening, 6. Other causes of neuromuscular weakness, 7. Non progressive or very rapidly progressing ALS (ALSFRS-R decline from disease onset to randomisation \leq 0.1 / month or \geq 1.2 / month)², 8. Non-invasive ventilation, 9. Tracheotomy,

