The safety results from the phase I study are reassuring and no serious adverse reactions are considered expected by the sponsor for the purpose of expedited reporting of suspected unexpected serious adverse reactions (SUSARs). However, human safety data with IFB-088 are limited to the results of this first-in-human study on healthy volunteers. Since IFB-088 has never yet been tested in ALS patients, who may present with potential additional risk factors linked to their condition, a set of measures will be implemented in this study in order to minimise those potential risks, including i) Restriction of eligibility criteria to patients with no other serious illness(es) or medical condition(s) such as cancer, cardiac, liver, renal or haematological diseases, ii) Regular monitoring of safety laboratory and clinical AEs in all patients enrolled in the present clinical trial, since as with any new drug, there is a risk that unidentified or unexpected side effects may occur, iii) Definition, monitoring and specific reporting procedure for AEs of special interest (AESIs), iv) Implementation of a data safety monitoring board (DSMB) for periodic benefit risk assessment.

In preclinical studies, kidneys appeared to be the only affected organs in Sprague Dawley rats at IFB-088 doses above the NOAEL (1.5 mg/kg/b.i.d., i.e. 3 mg/kg/day). Adverse, dose-related crystal nephropathy was observed in both sexes, but at slightly lower doses in males compared to females and was the first cause of moribundity and death. No signs of crystal nephropathy were reported in dogs and rabbits at dose levels of up to 16 mg/kg/day (i.e. 8 mg/kg b.i.d.) and 24 mg/kg/day (i.e. 12 mg/kg b.i.d), respectively. In the phase I P188 study no changes in the renal-associated biochemistry parameters and no IFB-088 related AEs from the renal system organ class were reported. Although the renal findings in the Sprague Dawley rat strain are not completely understood yet, the current data suggest that it likely represents a species-specific toxicity not representative of the risk in humans. Nonetheless renal toxicities will be reported in this study as AESIs and renal function will be closely monitored, along with microscopic examination of urine to detect crystals.

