5.2 EXCLUSION CRITERIA

A patient will not be eligible for inclusion in this study if at least one of the following criteria applies:

1. Known other significant neurological disease(s),
2. Serious illness(es) or medical condition(s) (e.g. unstable cardiac disease, cancer, hematologic disease, hepatitis or liver failure, renal failure) that is not stabilised or that could require hospitalisation and may jeopardise the participation in the study,
3. Abnormal renal function at screening defined as estimated glomerular filtration rate (eGFR) $< 60 \text{ mL/min}/1.73\text{m}^2$,

¹⁰ According to the CTFG guideline V2.1 September 2020, a woman is considered of childbearing potential (WOCBP), i.e., fertile, following menarche and until becoming post-menopausal unless permanently sterile. Permanent sterilisation methods include hysterectomy, bilateral salpingectomy and bilateral oophorectomy. A postmenopausal state is defined as no menses for 12 months without an alternative medical cause. A high follicle stimulating hormone (FSH) level in the postmenopausal range may be used to confirm a post-menopausal state in women not using hormonal contraception or hormonal replacement therapy. However, in the absence of 12 months of amenorrhea, a single FSH measurement is insufficient. A man is considered fertile after puberty unless permanently sterile by bilateral orchidectomy.

4. Abnormal liver function at screening defined as total bilirubin levels >1.5 ULN, and/or AST and/or ALT >3 ULN,
5. Neutropenia (ANC $<1.5 \times 10^9/L$) at screening,
6. Other causes of neuromuscular weakness,
7. Non progressive or very rapidly progressing ALS (ALSFRS-R decline from disease onset to randomisation ≤ 0.1 / month or ≥ 1.2 / month)¹¹,
8. Non-invasive ventilation,
9. Tracheotomy,
10. Dementia or other severe active psychiatric illness, including suicidal ideation assessed using the Columbia-Suicide Severity Rating Scale (C-SSRS),
11. Patient with a significant pulmonary disorder not attributed to ALS or who require treatments that might complicate the evaluation of the effect of ALS on respiratory function,
12. Patient treated by edaravone for ALS,
13. Patient using unauthorised concomitant treatments, namely moderate or strong inhibitors or inducers of CYP1A2, strong inhibitors or inducers of CYP2D6 or 2C19 and strong inhibitors of OCT2, as listed in [Section 6.2](#). Combined oral contraceptives containing ethinylestradiol are forbidden concomitant medications,

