5.4 Patient Disposition

Subject disposition will be summarized as follows:

- The number of patients who failed screening and the reasons for failure will be tabulated for the Screened Set.
- The number of patients who were screened, randomized, treated, randomized or treated (i.e. enrolled) and who are in each analysis set will be summarized by treatment group and overall for the Screened set.
- The number of patients completing the study and those prematurely discontinuing the study as well as the reasons for discontinuation will be tabulated by treatment group and overall.
- The number of patients present at each scheduled visit will be summarized by treatment group.
- The reasons for exclusion from the PPS will be summarized by treatment group and overall.
- Study duration (days) will be summarized by treatment group and overall in RS.
- Treatment duration (days) will be summarized by treatment group and overall in RS.

Early termination (ET) assessments as well as V3 bis will only be listed and not included in by-visit summary displays.

All patients disposition data will also be listed.

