5.12.1.2 Treatment emergent adverse events

The number of patients with at least one TEAEs and the corresponding number of events will be described by System Organ Class and Preferred Term overall in the safety population. In case a same patient presented the same AE (i.e. same event as defined according to SOC and PT) several times during the study, only one occurrence will be reported, but the total number of events will be counted. This table will be sorted by decreasing percentage of SOC and PT within SOC for the overall column.

The following listings will be edited in order to complete the AE analyses:

- All TEAE reported along the study
- TEAE related to study drug,
- Serious TEAE,
- Grade ≥ 3 (severe) TEAE,

STATISTICAL ANALYSIS PLAN		
InFlectis BioScience	Sponsor:	InFlectis BioScience
	Protocol Number:	P288ALS
VERSION 1.0 NOV 12, 2024		

- TAESIs

For each listing of AE, the following items will be included: Patient identifier, Country, Age (years), Sex, Start date of treatment - Reported term, MedDRA primary SOC, MedDRA preferred term, Start/end datetime of AE, Seriousness, Seriousness criteria, Relationship to study drug, Intensity, Outcome, Action taken regarding investigational drug, Corrective treatment, and if it is an AE of special interest.

In addition, for specific event of interest, a listing of patients with triglycerides > 5.7 mmol/L with at least 20% increase compared to baseline value will be provided. Triglycerides and Glomerular Filtration Rate will be described by classes defined in section 5.2.

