5.12.3.3 Analysis

Clinically significant abnormalities in laboratory values across the whole study will be summarized and listed.

For urinalysis parameters:

Shift tables in relation with normal, abnormal CS and abnormal NCS value from baseline to V3 and V4 will be presented for each parameter.

Urinalysis data will also be listed separately for each parameter.

For 24h protein test parameters:

Shift tables in relation with normal, abnormal CS and abnormal NCS value from baseline to V3 and V4 will be presented for the investigator's overall assessment.

STATISTICAL ANALYSIS PLAN			
InFlectis BioScience	Sponsor:	InFlectis BioScience	
	Protocol Number:	P288ALS	
VERSION 1.0 NOV 12, 2024			

A listing will also be presented for patients with at least one abnormal clinically significant of 24h protein test during the study.

For hematology, biochemistry, renal function, liver function and electrolytes parameters:

Each measurement (continuous data) will be categorized as below, within, or above normal range, based on ranges supplied by the laboratory used. Shift tables in relation to the normal range from Baseline to V3 and V4 will be presented for each parameter.

Laboratory data will also be listed separately for each parameter (indicating abnormal values at each applicable follow-up time point). Quantitative value at each visit with the change from baseline and relative change from baseline will be also presented in the listing.

Table 4: Specific rules for ULN and LLN by parameters

Parameter	Units	Below normal range	In normal range	Above normal range
Glomerular Filtration Rate	ml/min/1,73 m ²	<90	≥90	NA
Basophils	10 ³ /mm ³ ou 10 ³ /uL ou 10 ⁹ /L ou G/L	NA	<0.1	≥0.1
	%	Not analysable (will be converted by data management)		
Eosinophils	10 ³ /mm ³ ou 10 ³ /uL ou 10 ⁹ /L ou G/L	NA	<0.4	≥0.4
	%	Not analysable (will be converted by data management)		
Erythrocytes	10 ¹² /L, 10 ⁶ /mm ³ , 10 ⁶ /uL, T/L	<3.8	[3.8 ;5.5]	>5.5
Hemoglobin	g/dL	<12	[12 ;16]	>16
	g/L	<120	[120 ;160]	>160
Lymphocytes	10 ³ /mm ³ ou 10 ³ /uL ou 10 ⁹ /L ou G/L	<1,5	[1,500 ; 4]	>4
	%	Not analysable (will be converted by data management)		
Monocytes	10 ³ /mm ³ ou 10 ³ /uL ou 10 ⁹ /L ou G/L	<0.5	[0.5 ; 0.8]	>0.8
	%	Not analysable (will be converted by data management)		
Neutrophils	10 ³ /mm ³ ou 10 ³ /uL ou 10 ⁹ /L ou G/L	<1.5	[1.5 ; 7]	>7
	cells/mm ³	<1500	1500 et 7000	>7000

STATISTICAL ANALYSIS PLAN				
InFlectis BioScience	Sponsor:		InFlectis BioScience	
	Protocol Number:		P288ALS	

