VERSION 1.0 NOV 12, 2024				

	%	Not analysable (will be converted by data management)		
White blood cells, total	1000/uL, 10 ³ /mm ³ , 10 ³ /uL, 10 ⁹ /L et G/L	<4.5	[4.5 ; 11]	>11
Glucose	mg/dl	<70	[70 ; 110]	>110
	mmol/L	<4	[4 ; 6.1]	>6.1
	umol/L	<400	[400 ; 610]	>610
HDL cholesterol	g/L	<0.4	≥ 0,4	NA
	mg/dl	<40	≥ 40	NA
	mmol/L	<1.04	≥ 1.04	NA
LDL cholesterol	mg/dL	NA	<160	≥160
	mmol/L	NA	<4.1	≥4.1
Total Cholesterol	mg/dL	NA	<200	≥200
	mmmol/L	NA	<5	≥5
Triglycerides	g/L	NA	≤1.5	>1.5
	mg/dL	NA	≤150	>150
	mmol/L	NA	<1.71	>1.71
	umol/L	NA	<=171	>171
Alanine Aminotransferase	All units	NA	<ULN	>ULN
Aspartate Aminotransferase	All units	NA	≤ULN	>ULN
D-Dimers	All units	NA	≤ULN	>ULN
Direct Bilirubin	All units	NA	≤ULN	>ULN
Gamma Glutamyl Transferase	All units	NA	≤ULN	>ULN
Other parameters	All units	<LLN	[LLN ; ULN]	>ULN

If LLN is missing then all values below the ULN will be considered as in reference range.

If ULN is missing then all values above the LLN will be considered as in reference range.

If a value is <xx then:

- If the LLN = 0 or missing or NA then consider the value as in reference range
- Else consider the value as low reference range

If a value is >xx then:

- If the ULN is missing or NA then consider the value as in reference range
- Else consider the value as upper reference range

For Glomerular Filtration Rate:

If a value is >xx with xx<90 then consider value as below reference range

If a value is >xx with xx≥90 then consider value as in reference range

If a value is <xx then consider value as below reference range

STATISTICAL ANALYSIS PLAN		
InFlectis BioScience	Sponsor:	InFlectis BioScience
	Protocol Number:	P288ALS
VERSION 1.0 NOV 12, 2024		

Note: for all listing value of premature discontinuation and V3bis visit will be also presented when applicable.

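### The eGFR shift table cannot show further decline in patients who enter at eGFR 60–89, and all blood-laboratory shift tables use only V3 and V4

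*SAP*

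**What the plan says.** - SAP 5.12.3.3, for haematology, biochemistry, renal, liver and electrolyte parameters: "Shift tables in relation to the normal range from Baseline to V3 and V4 will be presented for each parameter".
- SAP Table 4 gives eGFR two classes, below 90 (below normal range) and 90 or more (in range). For censored results it adds: "If a value is >xx with xx<90 then consider value as below reference range". A laboratory report of >60 is therefore coded as below range.
- Protocol 5.2, exclusion criterion 3, excludes eGFR below 60 at screening, so patients at 60–89 may enter.
- SAP 5.2.22 defines six eGFR classes, from below 15 to 90 or more. Their only stated use is in SAP 5.12.1.2: "Triglycerides and Glomerular Filtration Rate will be described by classes defined in section 5.2". No visits, layout or cross-tabulation against baseline are given.
- SAP 5.12.3.2 derives reference-range classes at V1, V2 and V-FU as well as V3 and V4. It also notes eGFR and creatinine at V2 + 1 month, V3 + 1 month and V3 + 2 months.
- SAP 5.4: "Early termination (ET) assessments as well as V3 bis will only be listed and not included in by-visit summary displays". SAP 5.2.5 makes an exception for a discontinuation visit on days 83–99 (treated as V3) or 170–194 (treated as V4).
- Protocol 1.3, after describing crystal nephropathy in rats above the no-effect dose: "Nonetheless renal toxicities will be reported in this study as AESIs and renal function will be closely monitored".

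**The concern.** Safety is the primary objective, and renal toxicity is a named adverse event of special interest. A laboratory shift table should show how many patients in each arm got worse, and by how much. With one cut at 90 and an entry floor of 60, the eGFR table has no room for decline in the patients who start with the least renal reserve. It also counts trivial crossings of 90 as events.

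The V3/V4 restriction compounds this. The protocol schedules eGFR at months 2, 4 and 5 in addition to the hospital visits, and none of those results reaches a shift table. The same restriction affects liver and haematology results. Protocol 5.3 lists raised ALT or AST and neutropenia among its criteria for permanent drug discontinuation, so a patient's worst value may be recorded at a visit the tables leave out.

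**Working it through.** **1. The plan's own safety figure.** SAP section 3 gives the probability of at least one SAE among 28 treated patients as 76.2% at 5% incidence and 94.8% at 10%. From 1 − (1 − p)^28:

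- p = 0.05: 1 − 0.95^28 = 76.2%
- p = 0.10: 1 − 0.90^28 = 94.8%

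Both reproduce. The SAP states no operating figure for the shift tables.

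**2. Table 4 against the 5.2.22 classes.** Relative change = 100 × (follow-up − baseline) / baseline. Class labels are as printed in the SAP.

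| Baseline → follow-up | Change | Table 4 | 5.2.22 classes |
|---|---|---|---|
| 85 → 35 | −58.8% | below → below, no shift | 59–90 → 29–44 |
| 75 → 37 | −50.7% | below → below, no shift | 59–90 → 29–44 |
| 60 → 14 | −76.7% | below → below, no shift | 59–90 → below 15 |
| 91 → 89 | −2.2% | in range → below, shift | 90 or more → 59–90 |
| 95 → 45 | −52.6% | in range → below, shift | 90 or more → 44–59 |
| 120 → 91 | −24.2% | in range → in range, no shift | no change |
| 89 → 60 | −32.6% | below → below, no shift | no change |

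The finer classes recover the large falls in the first three rows. They do not recover 89 → 60 or 120 → 91.

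**3. Timepoints used.** Counted from the schedule of activities (protocol Table 2 and footnotes), protocol Table 3 and SAP 5.12.3.2:

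- eGFR: V1, V2, month 2, V3, month 4, month 5, V4, V-FU = 8. Two are used and 6 omitted (6/8 = 75%).
- Creatinine: the same 8 plus V0 + one week = 9. Two are used and 7 omitted (7/9 = 78%).
- Liver and haematology: V1, V2, V3, V4, V-FU = 5. Two are used and 3 omitted (3/5 = 60%).

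A patient withdrawn on, say, day 45 has no post-baseline entry in any of these tables.

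**4. Illustration of size (assumed inputs).** Let q be the share entering at 60–89. The documents do not give it, so 25%, 50% and 75% are used. Suppose that decline is independent of baseline eGFR, that every decline from 90 or more crosses 90, and that each is caught at V3 or V4. The chance that the eGFR shift table shows at least one affected patient among 28 is then 1 − (1 − p(1 − q))^28:

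| Incidence p | No blind group | q = 25% | q = 50% | q = 75% |
|---|---|---|---|---|
| 5% | 76.2% | 65.7% | 50.8% | 29.7% |
| 10% | 94.8% | 88.7% | 76.2% | 50.8% |

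These figures describe the eGFR shift table alone, not the trial's overall ability to notice renal harm.

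**The case against.** The strongest reply is that the eGFR table is one of several renal outputs:

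- Creatinine and blood urea nitrogen fall under the general lower/upper-limit rule of Table 4, so they can shift above the upper limit in any patient, whatever the entry eGFR.
- Urinalysis parameters and the 24-hour protein assessment have their own shift tables.
- Listings give each patient's value, change and relative change, including discontinuation-visit values, and in a 50-patient trial they can be read.
- Clinically significant laboratory abnormalities are summarised across the whole study. Protocol 4.2.1.1 requires such findings to be reported as adverse events, which are what the primary endpoints count.

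This stands, and it rules out the stronger reading that a reader might infer, namely that the laboratory shift tables cannot show renal toxicity at all. Patients entering at 90 or more can also shift in the eGFR table. Nor do the documents make the kidney the lead safety concern. Renal toxicity is one of three events of special interest (protocol 7.4), and protocol 1.3 regards the rat finding as probably species-specific.

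Two further inferences fail. A count of blinded patients cannot be drawn from the ages quoted in the protocol, because no document links age to baseline eGFR. The 59 in the 5.2.22 classes, against 60 for eligibility, may be only bracket notation lost in the text.

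The reply does not close the gap. The creatinine, blood urea nitrogen, urine and 24-hour protein shift tables share the V3/V4 limit. Change and relative change are assigned to listings, with no by-arm summary. The whole-study summary has no numeric criterion in the SAP, and for adverse-event reporting the protocol leaves clinical significance to the investigator. SAP 5.2.19 suggests preferred terms for hypotension and hypertriglyceridaemia but nothing for renal toxicity, and the adverse event summary in 5.12.1.1 has no special-interest row. Crystalluria is listed only.

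**Conclusion.** The point holds in limited form. The eGFR shift table cannot register any further fall in a patient entering at 60–89. That follows from the Table 4 rule and the eligibility floor and needs no assumption. The blood-laboratory shift tables omit 6 of 8 scheduled eGFR results, 3 of 5 liver and haematology results, and discontinuation values outside the two day windows. The other outputs cover this in part, but none is specified as an objective by-arm view of worst within-patient change.

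How many patients are affected is unknown, because baseline eGFR is not given. The probabilities in step 4 of the working are conditional on an assumed share and on simplifying assumptions about decline. The primary adverse event analysis is not invalidated. This is a weakness in how laboratory safety data are displayed, worth correcting because safety is the primary objective and renal toxicity is a named event of special interest.

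**What to change.** Amend SAP 5.12.3.3, and 5.2.22 where needed:

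1. For eGFR, tabulate by arm the shift from baseline to the worst post-baseline value using the 5.2.22 classes, written with non-overlapping boundaries and with the cut aligned to 60. State how censored results such as >60 are placed in those classes.
2. For renal, liver and haematology parameters, add a by-arm shift table from baseline to worst post-baseline value. Use every recorded scheduled, local-laboratory, unscheduled and discontinuation-visit result, and state for each parameter which direction counts as worst.
3. Summarise by arm, as well as list, the change and relative change in creatinine and eGFR. This is needed because the classes still miss falls such as 89 to 60.
4. Keep the V3 and V4 shift tables alongside these.

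The cost is SAP wording and table programming. No new assessment is required; unscheduled results enter only where they were recorded. Under SAP section 5 the change should be approved before the blind is broken. If it comes after final database lock, it belongs in a documented addendum.

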8. STATISTICS

8.1 STATISTICAL AND ANALYTICAL METHODS

8.1.1 General statistical considerations

Statistical analyses will be performed by the sponsor or under the supervision of the sponsor and further detailed in the SAP, which will be finalised prior to the unblinding of data and database lock.

In general, summary tabulations will be presented by treatment arm and will display the number of observations, mean, standard deviation (SD), median, Q1, Q3 quartiles, minimum, and maximum for continuous variables, and the number and percent per category for categorical data.

Patient disposition

An accounting of study patients by disposition will be tabulated and the number of patients in each analysis set will be summarised. Patients who discontinue study treatment and patients who withdraw from the study, with associated reason(s), will be summarised. A summary of protocol deviations by treatment arm and the corresponding listing by patient will be generated.

Nominal alpha level of significance

Unless otherwise noted, as the trial is a safety trial and an estimation efficacy study and not powered for efficacy endpoints, all tests performed on efficacy assessments will be conducted at a 1-sided nominal alpha level of 0.10 and confidence intervals (CIs) will be calculated at 80%, 2-sided 95% confidence intervals will also be provided.

Missing data handling

As a general rule, missing data will not be replaced. Sensitivity analyses based on multiple imputation will be proposed and further detailed in the SAP.

Multiplicity

As it is mainly an estimation trial, there is no adjustment for multiplicity.

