8.1.5 Efficacy / safety analysis

8.1.5.1 Primary outcome

Usual descriptive statistics will be used and detailed in the SAP to analyse the safety parameters.

AEs will be classified by system organ class and preferred term using the Medical Dictionary for Regulatory Activities (MedDRA). AEs will be listed and summarised by, MedDRA preferred term, severity, and relationship to study drug. In the event of multiple occurrences of the same AE with the same preferred term in one patient, the AE will be counted once as the occurrence.

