5.12.3.2 Expressions

For investigator's overall assessment of 24h protein test and urinalysis parameters, values will be expressed in class (Normal, Abnormal clinically significant (CS), Abnormal non clinically significant (NCS)) at baseline and at each post-baseline visit (baseline (V0), V1, V2, V3, V3bis, V4 and V-FU visit).

For hematology, biochemistry, renal function, liver function and electrolytes parameters, values will be expressed as following:

- in class according to reference ranges at each visit (Low, In range or High) at baseline and at each post-baseline visit (baseline (V0), V1, V2, V3, V4 and V-FU visit)
- quantitatively with value at baseline, at each post baseline visit, change from baseline to each post baseline visit and relative change from baseline to each post baseline visit for listing value

Note:

- for creatinine and Glomerular Filtration Rate, other visits are performed: V2 + 1 month, V3 + 1 month, V3 + 2 months
- And for urine dipstick: V0 + 1 week

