5.12.4.3 Analysis

Descriptive statistics for observed values and changes from Baseline in the following vital signs will be presented by treatment group and visit.

All vital signs data will also be listed. Value of premature discontinuation and V3 bis visit will be also presented when applicable.

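### Blood laboratory values get only three-class shift tables at V3 and V4 and otherwise go to listings, with no numerical summary by arm specified and no declared departure from the general rules of the protocol and SAP

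*SAP*

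**What the plan says.** SAP 5.12.3.3 treats the five blood panels (haematology, biochemistry, renal, liver, electrolytes) in one way: "Each measurement (continuous data) will be categorized as below, within, or above normal range, based on ranges supplied by the laboratory used". The tables follow from that: "Shift tables in relation to the normal range from Baseline to V3 and V4 will be presented for each parameter". On the measured values it says: "Quantitative value at each visit with the change from baseline and relative change from baseline will be also presented in the listing". SAP 5.12.3.2 agrees, since its quantitative expression ends with "relative change from baseline to each post baseline visit for listing value".

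Other tabulated output touches these data:

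- Clinically significant abnormalities over the whole study are summarised (SAP 5.12.3.3).
- Triglycerides are described in five classes and GFR in six (SAP 5.2.22 and 5.12.1.2).
- Creatinine is in the biomarker list (SAP 5.11.5.1) and would get geometric means on the FAS. Whether this is blood creatinine is not stated.

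The general rules point the other way. Protocol 8.1.1 sets the default: "In general, summary tabulations will be presented by treatment arm and will display the number of observations, mean, standard deviation (SD), median", followed by quartiles and extremes. Protocol 8.1.5.1 adds: "Usual descriptive statistics will be used and detailed in the SAP to analyse the safety parameters". SAP 5.3 likewise has continuous variables summarised numerically. For vital signs, SAP 5.12.4.3 applies the rule: "Descriptive statistics for observed values and changes from Baseline in the following vital signs will be presented by treatment group and visit". SAP 5.12.5.3 does the same for ECG. SAP section 7 lists two changes from the protocol, and neither concerns laboratory data.

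**The concern.** Safety is the primary objective, and SAP 2.2.1 names laboratory parameters among the safety endpoints. In a trial of 50 patients randomised 2:1, a moderate systematic drift in an analyte moves few patients across a reference limit, but it would show in a by-arm table of change from baseline. With listings alone, the reader of the study report must build that table by hand. The gap matters most for the kidney, the only affected organ in the rat studies (protocol 1.3), and for the liver, where protocol 1.3 notes the hepatotoxicity of background riluzole. Protocol 3.1 adds creatinine and eGFR draws at months 2, 4 and 5, yet no numerical summary is specified for them.

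**Working it through.** **1. What the specified tables cannot show.** The limits come from SAP Table 4 (5.12.3.3) and the GFR classes in SAP 5.2.22. Percentage change = 100 × (new − old) / old.

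| Parameter | Change | Arithmetic | Class before and after |
|---|---|---|---|
| Haemoglobin, g/dL | 16 to 12 | −4/16 = −25% | in range, in range |
| Neutrophils, 10⁹/L | 7 to 1.5 | −5.5/7 = −79% | in range, in range |
| White cells, 10⁹/L | 11 to 4.5 | −6.5/11 = −59% | in range, in range |
| eGFR, mL/min/1.73 m² | 89 to 60 | −29/89 = −33% | below, below; also stays in the finer class from 59 to under 90 |

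ALT has a single class above ULN, so 1.1 × ULN and 5 × ULN are the same entry. The protocol itself distinguishes levels above the limit: 3 × ULN in exclusion criterion 4 and 5 × ULN in section 5.3.

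**2. Which time points are missing.** SAP 5.12.3.2 defines classes at V1, V2, V3, V4 and V-FU and notes extra creatinine/GFR draws at V2 + 1 month, V3 + 1 month and V3 + 2 months. The shift tables in 5.12.3.3 use V3 and V4 only. SAP 5.4 keeps early-termination assessments out of by-visit displays, unless SAP 5.2.5 maps the visit to V3 or V4.

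**3. The plan's own figures.** 42/(1 − 0.15) = 49.4, so 50 randomised, about 33:17. With 28 patients on IFB-088, 1 − 0.95²⁸ = 76.2% and 1 − 0.90²⁸ = 94.8%. Both stated probabilities reproduce, and this point changes neither.

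**4. Illustration of the information lost.** Assumed, because the documents do not give them: a normal (or log-normal) analyte, a shift of 0.6 SD on IFB-088, a baseline-to-visit correlation r of 0.3 to 0.7, and a limit exceeded by 10%, 20% or 30% of patients at baseline. The two-sided 0.20 level is borrowed from SAP 5.11.1.1, which applies to efficacy.

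For change from baseline, the SD of change is √(2(1 − r)) and power ≈ Φ(0.6 / [SD of change × √(1/33 + 1/17)] − 1.282), with √(1/33 + 1/17) = 0.2985.

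- r = 0.7: SD 0.775; 0.6/(0.775 × 0.2985) = 2.59; Φ(1.31) = 0.90
- r = 0.5: SD 1.000; 2.01; Φ(0.73) = 0.77
- r = 0.3: SD 1.183; 1.70; Φ(0.42) = 0.66

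Simulation (20,000 trials per setting) agrees: about 0.65 to 0.90 over this range. For the count of patients moving from in range to high, the same simulated trials give 0.35 to 0.46 with Fisher's test and 0.47 to 0.53 with chi-square. At r = 0.7 and a 20% limit, the expected counts are 7.9 of 33 against 1.5 of 17.

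With the 28:14 evaluable patients of protocol 8.1.2 and r = 0.7, √(1/28 + 1/14) = 0.3273 and power is Φ(0.6/(0.775 × 0.3273) − 1.282) = Φ(1.08) = 0.86, against 0.27 to 0.33 for Fisher.

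**The case against.** The case for the SAP has four parts.

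- **Not everything is cut to three classes, and crossings are shown.** A reader might infer that every blood variable is reduced to low, in range or high, and that even movement across a limit is hidden. The documents do not support that. Triglycerides and GFR get finer classes, patients with triglycerides above 5.7 mmol/L and a rise of at least 20% are listed, crossings at V3 and V4 appear in the shift tables, and clinically significant abnormalities are summarised. Protocol 4.2.1.1 also requires clinically significant values to be reported as AEs. This part of the objection stands.
- **The protocol promised nothing specific.** Its rule is introduced as a general one and leaves the safety detail to the SAP, and its listed primary endpoints are adverse events, not laboratory means. So breach of promise is too strong. An undeclared departure from the stated default remains.
- **SAP 5.3 already covers it.** That section can be read as still requiring numerical summaries. The specific text in 5.12.3.2 and 5.12.3.3 sends the values to listings, so the sections conflict at best and a programmer would follow the specific one.
- **No laboratory test is planned.** This is correct, so the power figures compare two tests that nobody will run. A reader might also infer a uniform loss of 30 points or more. That fails: at r = 0.3 and a 0.4 SD shift the comparison is 0.44 to 0.45 against 0.33 to 0.34 (chi-square), about 11 points.

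No data are lost either, since every value is listed.

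**Conclusion.** The point holds as a gap in the safety reporting and an internal inconsistency that should be corrected. No by-arm numerical summary of value or change is specified for the blood safety parameters, with creatinine as a biomarker on the FAS the one possible exception. What goes unsummarised is movement within a class, size beyond a limit, and values at visits other than V3 and V4. This follows from the text and needs no assumption. The SAP gives no reason for treating laboratory data differently from vital signs and ECG, and section 7 does not record the choice.

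The size of the information loss depends on assumed shifts, correlations and out-of-range rates. The illustration shows that it can be substantial in a trial of this size, but it is not a property of the plan. Numerical summaries would not be precise either: for a difference in mean values at 28:14 the 95% CI half-width is 2.02 × 0.3273 = 0.66 SD.

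**What to change.** In SAP 5.12.3.3, add for each quantitative blood parameter a descriptive table by arm and visit of value and change from baseline, with n, mean, SD, median, Q1, Q3, minimum and maximum. Cover V1, V2, V3, V4 and V-FU, and for creatinine and eGFR the draws at months 2, 4 and 5. Show liver enzymes also as multiples of ULN. Keep the shift tables and listings. Reword 5.12.3.2 so that the quantitative expression is no longer tied to listings, which brings it into line with SAP 5.3. If the sponsor prefers listings only, state this in section 7 with a reason.

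Between-arm confidence intervals are optional: neither document plans inferential safety analysis, and intervals for every analyte at every visit would be numerous and unadjusted.

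The cost is a wording change and one standard table program, on data already collected and listed. The downside is more output pages.
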